4.4.2 Phase II Studies

Currently there are two clinical phase II studies with MV-CHIK going on. One in Europe (MV-CHIK-202; EudraCT: 2015-004037-26) and one in Puerto Rico (MV-CHIK-204; NCT03101111).

MV-CHIK-202:

This phase II study of MV-CHIK is being conducted at four sites across Austria and Germany. It is comparing 2 doses (5×10^4 and 5×10^5 TCID₅₀) of MV-CHIK administered at two different intervals (1 month and 6 months). Each of these four cohorts will have 70 consented subjects of which 60 will receive MV-CHIK and 10 will receive a licensed MMR vaccine as a comparator. In addition, two cohorts of 20 consented subjects each will receive MMR either one month or 6 months before MV-CHIK in order to assess the effect of recently boosted immunity to Measles on Chikungunya immunogenicity.

A database snapshot was performed in August 2017, providing preliminary interim safety and immunogenicity data up to study day 56.

Safety Analysis:

Until the database snapshot, overall 624 adverse events (AEs) were observed in 263 treated subjects, whereas 456 AEs [73.1%] were solicited by the means of a subjects' diaries and 168 unsolicited [26.9%], reported spontaneously. The intensity was mostly assessed as mild in 468 cases [75.0%] or moderate in 145 cases [23.2%] and 11 cases [1.8%] were classified as severe, disregarding relatedness.

Solicited AEs occurred more often in MV-CHIK group (91 subjects [72.7%]) compared to the control group (17 subjects [34.0%]) but unsolicited AEs were seen more frequently in the control group (17 subjects [34.0%] and 69 subjects [32.4%] in the MV-CHIK group respectively).

The most common solicited, systemic adverse event after immunisation was headache, which was reported by 42 subjects [19.7%] of the MV-CHIK group and by 10 subjects [20.0%] of the

control group. The severity of headache was mostly reported as mild (52 cases [65.0%]) or moderate (23 [28.8%]), 2 subjects reported severe headache.

After headache the most common solicited, systemic adverse events were observed in the following number of subjects: fatigue (33 [14.4%] MV-CHIK; 3 [8.8%] control group), flu like symptoms (16 [7.9%] MV-CHIK; 1 [2.9%] control group), nausea (14 [6.1%] MV-CHIK; 3 [8.8%] control group) and myalgia (14 [6.1%] MV-CHIK; 3 [8.8%] control group). Taken together, the frequency of solicited systemic AEs was equally distributed between MV-CHIK and control group.

This clinical phase II study (NCT03101111) initiated in May-2017 and currently conducted in Puerto Rico, a previously epidemic area, evaluates the safety and immunogenicity of MV-CHIK in 100 subjects. The main objective is to determine the safety of MV-CHIK administered in 2 doses (5×10^4 and 5×10^5 TCID₅₀) separated by 28 days in previously exposed versus unexposed individuals. The subjects will be randomised in a double-blind fashion to receive either MV-CHIK or the licensed active measles, mumps, and rubella vaccine (Priorix[®]) in a 4:1 ratio. Additionally, immunogenicity of MV-CHIK will be investigated in previously exposed versus unexposed individuals by a neutralisation assay.

4.5 Study Rationale

The current phase II trial is designed to investigate the immunogenicity, safety and tolerability of MV-CHIK as well as the long-term durability of anti-Chikungunya antibody response after administration of different dose levels of MV-CHIK in three different formulations.

The concentrations of the evaluated doses are 5×10^4 (± 0.5 log) TCID₅₀/dose, 1×10^5 (± 0.5 log) TCID₅₀/dose and 1×10^6 (± 0.5 log) TCID₅₀/dose and the compared formulations are lyophilised, liquid frozen and liquid SPS[®] (Stabilising and Protecting Solution), respectively.

The induction of functional anti-Chikungunya antibodies by MV-CHIK will be investigated in healthy adults aged 18 to 55 years, by means of immunoassays like ELISA and T-cell assay and PRNT₅₀. The timepoint day 28 and day 56 after immunisation were found to be suitable for immunogenicity analyses to reveal valuable information on future treatment recommendations (single shot treatment vs. double immunisation).

A randomised, observer-blinded study design was chosen to allow an objective recording and assessment of all adverse events.

The MV-CHIK doses used in previous clinical trials (phase I and phase II) was calculated between 1.5×10^4 (± 0.5 log) - 5×10^5 (± 0.5 log) TCID₅₀/dose. This dose was efficient to induce a seroconversion rate of up to 96% in the study population. To further investigate the capacity of the vaccine to induce sufficiently high neutralising titres and seroconversion rates after a single immunisation, an increased dose 1×10^6 (± 0.5 log) TCID₅₀/dose will be administered once or twice.

The different vaccination schedules, two MV-CHIK vaccinations on days 0 and 28 or one MV-CHIK vaccination on day 0 and placebo on day 28, allow to compare the immunogenicity of these dosing regimens. A single shot or two vaccinations within a short period of time are desirable to allow for a quick immunisation before travelling to areas with active transmission of the Chikungunya virus.

In addition to the previously tested liquid frozen and lyophilised formulations, Themis has an ongoing project to improve the product stability in a variety of potential formulations. Recently, a liquid formulation (stored at 2-8°C) showed promising stability data. Clearly, a liquid formulation will substantially decrease the costs of good and will facilitate the use of the vaccine throughout the world. Thus, a group of subjects will receive the SPS formulation and safety and immunogenicity will be analysed.

The induction of virus specific T cells is a critical step in the generation of a functional immune response. For this purpose, the rate of Chikungunya virus specific T cells will be analysed in vitro.

Additionally, the study design will allow for the first time to gather data on the long-term stability of specific antibodies, by testing serum samples 6 months and 1 year after the first immunisation with MV-CHIK.

Up to now the level of protective anti-Chikungunya-Ab titre could only be estimated. Therefore, it is of special interest to evaluate and proof Ab titres that are able to prevent CHIKV infections. The design of the study will allow to collect human serum samples, to verify efficacy, by passive transfer of antibodies to non-human primates in future investigations.

This study was designed according to the Note for Guidance on Clinical Evaluation of New Vaccines (CHMP/VWP/164653/2005), where applicable, and will be conducted in compliance with the protocol, Good Clinical Practice (GCP) as set forth in the International Council on Harmonisation (ICH) guidelines on GCP (ICH E6), and applicable local regulatory requirements.

4.6 Benefit/Risk Assessment

General

Potential risks that are frequently associated with vaccination are the occurrence of local reactions such as oedema, induration and erythema, transient local pain or tenderness at the injection site as well as mild to moderate headache, myalgia, flu-like symptoms or fatigue. Vaccines have been known to induce allergic and anaphylactic reactions apart from reactions at the vaccination site and systemic flu-like reactions. Additionally, needle picks for blood sampling may cause discomforts and local reactions.

MV-CHIK Related

As described above, adverse events (AEs) previously reported with MV-CHIK include injection site pain, headache, fatigue, and joint pain or arthralgia. Refer to the current version of the Investigators' Brochure for more detail.

Potential for Severe Adverse Reaction

In the past, a live virus vaccine against Chikungunya virus, which was based on an attenuated Chikungunya-strain was associated with mild, transient arthralgia in immunised individuals. The MV-CHIK vaccine is based on live measles virus and contains no live Chikungunya virus. Therefore, induction of chikungunya-like symptoms is not expected. However, the subjects will be monitored for occurrence of arthralgia, an adverse event of special interest (AESI).

Potential Benefit

If the clinical development of MV-CHIK is successful, the potential benefit of MV-CHIK vaccination would be life-long protection against Chikungunya infection helping people, who are at risk of acquiring a possibly life-threatening infection with CHIKV.

A boost in measles immunity may be an additional benefit.

Conclusion

The benefit risk ratio is considered favourable.

5. TRIAL OBJECTIVES AND MEASUREMENTS

5.1 Primary Objective

- To investigate immunogenicity and safety of MV-CHIK in different dose regimens, 28 days after one or two vaccinations

The immunogenicity will be determined by means of PRNT₅₀ 28 days after a single shot treatment at Visit 3 (study day 28) and 28 days after two treatments with MV-CHIK at Visit 5 (study day 56). Local and systemic AEs will be recorded and assessed.

5.2 Secondary Objectives

- To compare immunogenicity, safety and tolerability between different doses and formulations of MV-CHIK during the treatment period up to day 56
- To investigate the immunogenicity and safety of a novel liquid vaccine formulation

To cover this objective immunogenicity will be determined by means of PRNT₅₀ at the following timepoints during the treatment period: Visit 1 (day 0), Visit 3 (day 28) and Visit 5 (day 56). Solicited and unsolicited AEs will be recorded at each visit during the treatment period.

- To evaluate cellular responses induced by one or two immunisations

The cellular response will be investigated by T cell analysis of PBMCs isolated at Visit 1(day 0), Visit 2 (day 14), Visit 3 (day 28), Visit 4 (day 42) and Visit 5 (day 56)

- To evaluate the long-term immunogenicity of MV-CHIK up to one year after the first MV-CHIK treatment.

The long-term immunogenicity will be observed by means of PRNT₅₀ detecting anti-Chikungunya antibodies 6 months and one year after the first treatment with MV-CHIK (at Visit 6 and Visit 7).

- To collect human sera for future efficacy evaluation, by passive transfer of anti-Chikungunya antibodies to virus susceptible non-human primates

On study day 0 (Visit 1), day 28 (Visit 3), day 56 (Visit 5) and day 365 (Visit 7) blood samples will be collected for isolation of anti-Chikungunya antibody containing human serum.

6. TRIAL DESIGN

6.1 Overall Study Design

This is a prospective, interventional, observer-blinded, block-randomised, phase II trial, comparing different dose levels of MV-CHIK in three different formulations (lyophilised, liquid frozen and liquid SPS[®]) to evaluate immunogenicity, safety and tolerability of this novel Chikungunya vaccine. Placebo (physiological saline solution) will be applied to blind two different treatment schedules, evaluating single shot versus double shot treatment.

The study will be conducted at a single study site, Celerion in Belfast (United Kingdom) and is registered online at <http://www.ClinicalTrials.gov> under EudraCT number 2018-000211-25.

After the screening procedures, 60 healthy male and female volunteers aged 18-55 years will be randomly assigned to one of five treatment groups (A, B, C, D or E). Subjects will be observed for safety and immunogenicity for 56 days during the treatment period, starting with the first MV-CHIK vaccination at Visit 1 (day 0) up to Visit 5 (day 56). After this treatment period subjects will return to site at Visit 6 (after 6 months) and at Visit 7 (after 1 year) for collection of serum to follow up the durability of specific antibodies against Chikungunya.

The investigator and site personnel assessing AEs, all subjects, as well as the sponsor's representatives involved in the monitoring and conduct of the study will be blinded to which vaccine was administered. Only the site personnel performing randomisation, preparation and administration of IMP will be unblinded.

6.2 Study Endpoints

6.2.1 Primary Endpoint

- Immunogenicity 28 days after the last MV-CHIK vaccination confirmed by the presence of functional antibodies as determined by the plaque reduction neutralisation test (PRNT₅₀)

6.2.2 Secondary Endpoints

- Rate of solicited and unsolicited adverse events during the treatment period until day 56
- Serious adverse events during the treatment period until study day 56
- Immunogenicity on days 0, 28 (group A, B, C, and D), days 0, 56 (group E) and long-term immunogenicity on day 182 (6 Mo) and 365 (12 Mo), confirmed by the presence of functional antibodies as determined by the plaque reduction neutralisation test (PRNT₅₀).
- Measurement of anti-Chikungunya antibodies on days 0, 28, 56, 182 and 365 determined by enzyme linked immunosorbent assay (ELISA)
- Measurement of anti-Measles antibodies on days 0, 28, 56 determined by enzyme linked immunosorbent assay (ELISA)
- Induction of Chikungunya specific immune responses on days 0, 14, 28, 42 and 56 determined by T-cell assay.

- Safety laboratory parameters (haematology, serum chemistry, coagulation, urinalysis)

6.3 Treatment Groups

After the screening procedure, 60 subjects eligible for the study will be randomised to one of the following 5 treatment groups:

Group A:

two vaccinations with MV-CHIK lyophilised formulation, low dose, on day 0 and day 28

Group B:

two vaccinations with MV-CHIK liquid frozen formulation, low dose, on day 0 and day 28

Group C:

two vaccinations with MV-CHIK liquid SPS® formulation, low dose, on day 0 and day 28

Group D:

two vaccinations with MV-CHIK liquid frozen formulation, high dose, on day 0 and day 28

Group E:

one vaccination with MV-CHIK liquid frozen formulation, high dose on day 0 and placebo on day 28

The concentration of different MV-CHIK dose levels per treatment group are:

Group A: low dose: $5 \times 10^4 \pm 0.5 \log \text{TCID}_{50}$ /dose

Group B+C: low dose: $1 \times 10^5 \pm 0.5 \log \text{TCID}_{50}$ /dose

[figure not shown]
Group D+E: high dose: $1 \times 10^6 \pm 0.5 \log \text{TCID}_{50}$ /dose

The actual vaccine dosages are dependent on the manufacturing process, specifying and allowing a window of $\pm 0.5 \log$. The five different treatment groups, group sizes and vaccination schedules are summarised in table 1.

Table 1: Treatment Groups and Vaccination Schedule

Treatment Group	N	Vaccine	Formulation	Vaccine on day	Placebo on day
A	12	MV-CHIK $5 \times 10^4 (\pm 0.5 \log) \text{TCID}_{50}$	lyophilised	0 + 28	
B	12	MV-CHIK $1 \times 10^5 (\pm 0.5 \log) \text{TCID}_{50}$	liquid frozen	0 + 28	
C	12	MV-CHIK $1 \times 10^5 (\pm 0.5 \log) \text{TCID}_{50}$	liquid SPS®	0 + 28	
D	12	MV-CHIK $1 \times 10^6 (\pm 0.5 \log) \text{TCID}_{50}$	liquid frozen	0 + 28	
E	12	MV-CHIK $1 \times 10^6 (\pm 0.5 \log) \text{TCID}_{50}$	liquid frozen	0	28

6.4 Study Flowchart

6.5 Study Procedures

Table 2: Study Procedures

Visit	Screening	Treatment Period					Follow up Period		ET
		V1	V2	V3	V4	V5	V6	V7	
Study Day	-28 to -1	0	14 ±1	28 ±5	42 ±5	56 ±5	182 ±14	365 ±14	(7)
Informed Consent	X								
Inclusion/Exclusion Criteria	X	X							
Medical History	X	X							
Vaccination History	X								
Vital Signs (1)	X	X		X			X		X
Physical Examination (2)	X	X		X			X		X
Adverse Events (3)		X	X	X	X	X			X
Concomitant Medication (4)	X	X	X	X	X	X			X
Clinical Laboratory (5)	X			X			X		X
Pregnancy Test	X	X		X			X		X
Study Treatment (8)		X		X					
Dispense subject diary		X		X					
Collect subject diary			X		X				X
Local Tolerability (6)		X	X	X	X	X			X
Immunogenicity (PRNT ₅₀)		X		X		X	X	X	X
T-cell Immunity		X	X	X	X	X			X
CHIKV-antibodies (ELISA)		X		X		X	X	X	X
Measles-antibodies (ELISA)		X		X		X			X
Serum collection for passive transfer		X		X		X		X	X

(1) Assessment of vital signs will include systolic and diastolic blood pressure, pulse rate and body temperature

(2) A full physical examination will be performed at screening and a system based physical examination will be done at Visit 1, 3 and 5, if necessary according to findings in a symptom-directed physical examination

(3) Conditions/symptoms noted prior to first IMP administration will be reported as medical history and not as AEs, At Visit 6 and 7 AEs will not be recorded as subjects are allowed to participate in other clinical studies during the follow-up period.

(4) Medications administered within 30 days prior to screening until end of treatment period will be documented as concomitant medication.

(5) Clinical Laboratory parameters include:

- Virology: HB s-Ag, anti-HB c-Ab, anti-HC-Ab, HIV-Ab (only once at screening)
- Haematology: haemoglobin, haematocrit, erythrocyte count, differential and total white blood count, platelets
- Chemistry: creatinine, potassium, sodium, calcium, AST, ALT, alkaline phosphatase, bilirubin
- Coagulation parameter: prothrombin time (PT), activated partial thromboplastin time (aPTT), fibrinogen
- Urinalysis: pH-value, glucose, protein, bilirubin, urobilinogen, blood, leucocytes esterase, nitrite, ketone and specific gravity. In case of abnormal findings, a microscopy will be done for confirmation.

Please refer to section 8.11.1

(6) Local tolerability to be investigated 2 hours after each vaccination and additionally at the subsequent visits and prior to IMP administration.

(7) If the early termination occurs within the treatment period (at or before Visit 5), subjects shall perform all procedures as defined for Visit 5. If the early termination occurs within the follow up period (after Visit 5), subjects shall perform all procedures defined for Visit 7

(8) Administration of IMP will be performed according to allocated treatment group, after randomisation at Visit 1

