10.2 Recording of Adverse Events

All AEs occurring during the treatment period starting after the first vaccination at Visit 1 until termination of Visit 5 (day 56) observed by the investigator or reported by the subject (verbally or in the subject diary), will be recorded, whether or not related to the study treatment.

AEs will be requested at each visit during the treatment period up to Visit 5 (day 56) and additionally solicited by a subject's diary for 7 days after each vaccination. (see section 11.7)

The subjects will be asked generally (e.g. "How are you?") as well as specifically (e.g. "Have you experienced any problems since the last visit?").

The investigator must record all adverse events in the eCRF. One single adverse event page must be used per adverse event, from start to resolution, stating the following information: AE description, date of onset and end date, severity, relatedness, seriousness and action taken. Please consider definitions of section 10.1. Follow-up information should be provided as necessary.

If possible, the investigator should record the diagnosis. If a diagnosis is not available, the investigator should record each sign and symptom as individual adverse events. However, as soon as a diagnosis becomes available, all signs and symptoms should be summarised and replaced by the underlying adverse event term (e.g. common cold instead of separate AEs for headache, rhinorrhoea, arthralgia, fever etc.)

The AE should be documented stating the highest severity (i.e. if an AE goes from mild severity to moderate severity or vice versa, the whole episode of the AE should be reported with the moderate severity). Please consider Table 5 and 6 for grading local injection site reactions and systemic reactions.

For causality reporting purposes, the categories "definitely", "probably" and "possibly" qualify an event as "suspected" adverse reaction. AEs with missing causality assessment will be regarded as possibly related unless further specified.

Any medical condition that is present at screening will be considered as medical history and not reported as an AE. However, if the subject's condition deteriorates at any time during the study, it will be recorded as an AE.

It will be left to the investigator's clinical judgment to decide whether an AE requires the subject's removal from the study. In case of discontinuation, the subject will undergo an early termination visit.

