10.3 Reporting of Serious Adverse Events

The investigator should report all SAEs occurring during the treatment period (whether or not related to the IMP) within 24 hours of the site study team becoming aware of the event, to the Assign Safety Desk by completing an SAE Report Form.

The completed SAE Report Form should be submitted to the Assign Safety Desk either by fax or as pdf per e-mail:

Fax: PPD [REDACTED]

Email: PPD [REDACTED]

For urgent questions, please call the 24-hours Safety Hotline: PPD [REDACTED]

Under certain circumstances, the first notification can be done by phone, nevertheless, a written Serious Adverse Event Report Form should be submitted for confirmation to Assign Safety Desk.

After the initial SAE report the investigator will follow up proactively each subject and provide further information like copies of hospital case reports, laboratory reports or autopsy reports, to the Assign Safety Desk within 24 h after receipt.

Assign Safety Desk will assess initial and follow-up SAE reports from the site for expectedness, which will be determined based on the most recent edition of the Investigator's Brochure.

Reports of suspected unexpected serious adverse reactions (SUSARs) will be reported in an expedited manner to the regulatory authorities as required per local regulations within the required time frame.

The original copy of the SAE Report Form and the fax confirmation sheet must be kept with the documentation at the study site. Each SAE has also to be documented in the eCRF as a serious adverse event in the corresponding AE section.

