11.5 Post Vaccination Reactogenicity Assessments

All subjects enrolled in the study and who receive at least one study treatment (MV-CHIK or placebo) will be followed up 28 days after each study treatment. Solicited and unsolicited AEs will be recorded at each visit until the end of the treatment phase at Visit 5.

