6.2.2 Derivations and Definitions

- All solicited and unsolicited Adverse Events up to day 56 (Visit 5) will be analyzed for the preliminary analysis. AE reporting and documentation is completed at Day 56. Thus all AE in the database are considered for the adverse event endpoints. In case of unexpected data change, new reported AEs or follow-up information, affected tables and/or listings may be repeated for the final analysis. Otherwise,

Adapted from:

STAT03_A Statistical Analysis Plan

Version 6.0, Effective Date 16-Feb-2018

Confidential and intellectual property of Assign DMB. No part of this document or its contents may be duplicated, referenced, published or otherwise disclosed in any form or by any means without prior written consent of Assign DMB.

Page 16 of 29

06CJDX

adverse event tables are not repeated at the final analysis. This decision may be done in a DRM prior to database closure, see [Section 2.9](#).

- Percentages for AE rates are based on N (treatment group totals).
- Medical Conditions/symptoms noted prior to first IMP administration will be reported as medical history and not as adverse events. In case of an incomplete start date where it cannot clearly be decided if the Adverse Event started before the first IMP the Adverse Event will be considered to be started before first IMP.
- An Adverse Events is considered to be related to study treatment if “Relationship to Study Treatment” is answered with “definitely”, “probably” or “possibly” or the causality is missing.
- Adverse Events where an action was taken are considered if “Action taken with Study Treatment” is answered with “Second IMP Administration Delayed” or “Second IMP not Administered”.
- Tables showing “severe” events will include events with grade 3 or 4 or missing grade.
- In tables showing subjects with AEs by maximum severity, subjects will be counted only in the highest grading category, but events will be counted in each reported grading category.
- In tables showing AEs by causality, subjects will be counted only in the strongest relationship category, but events will be counted in each category.

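### New-onset SAEs and new-onset arthralgia, the named AESI, are not collected after Day 56, although all subjects are scheduled to return at Days 182 and 365

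*Combined protocol and SAP*

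**What the plan says.** The cut-off for new safety events is the same throughout the documents.

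- Protocol section 6.5, Table 2, footnote 3: "At Visit 6 and 7 AEs will not be recorded as subjects are allowed to participate in other clinical studies during the follow-up period". The SAP schedule (section 1.6) repeats this footnote.
- Protocol section 10.2 limits AE recording to the period from the first vaccination to the end of Visit 5.
- Protocol section 10.3: "The investigator should report all SAEs occurring during the treatment period (whether or not related to the IMP) within 24 hours".
- Protocol section 6.2.2 lists as a secondary endpoint "Serious adverse events during the treatment period until study day 56".
- SAP section 6.2.2: "AE reporting and documentation is completed at Day 56".
- Protocol section 11.5 states that treated subjects "will be followed up 28 days after each study treatment".

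Protocol section 4.6 names arthralgia as an AESI to be monitored but gives it no collection window of its own. Sections 8.6.1 and 8.6.2 schedule Visits 6 and 7 for all subjects and list only blood sampling there.

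Two things do continue past Day 56. Section 10.4 follows AEs and SAEs already recorded until they resolve or settle, or until the study ends. Section 10.6 follows pregnancies that begin before Day 56 to their outcome.

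**The concern.** The footnote's reason is that subjects may join other studies after Day 56. That makes a late event harder to attribute, but it has no bearing on whether the event happened. Attribution could be handled by recording the other product next to the event. Instead the plan asks nothing at two visits that subjects are due to make in any case.

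The trial adds a dose level above the range used before (section 4.5: earlier trials went up to 5×10^5 TCID50, here 1×10^6) and a new liquid formulation (section 4.5). In the first phase I study, AEs rose with dose, and severe and serious AEs occurred only in MV-CHIK recipients (section 4.4.1). An SAE or joint complaint that first appears between Day 56 and Day 365 would normally not reach the safety tables. For that period the study report could say only that events were not sought.

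**Working it through.** **Inputs**

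- Second injection at Visit 3: Day 28, window Days 23 to 33 (section 8.5.3).
- Last AE visit, Visit 5: Day 56, window Days 51 to 61 (section 8.5.5).
- Visits 6 and 7: Days 182 and 365 (section 8.6).
- Group sizes: 12 per group, so 48 in Groups A-D and 12 in Group E. Group E receives MV-CHIK on Day 0 only and placebo on Day 28 (section 6.3).

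**1. The plan's own figures.** 56 − 28 = 28 days, as in section 11.5. (365 − 56)/7 = 44.1 weeks, which agrees with the 44-week follow-up period in the synopsis.

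**2. New-onset collection after the last MV-CHIK dose**

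- Groups A-D: nominally 28 days. Both visit windows are counted from Visit 1, so the shortest interval is 51 − 33 = 18 days and the longest is 61 − 23 = 38 days.
- Group E: nominally 56 days (51 to 61) after its only MV-CHIK dose, and 28 days after placebo.

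**3. Time without new-onset collection.** 365 − 56 = 309 days, and 309/365 = 85% of time on study. In Groups A-D, 28 of the 365 − 28 = 337 days after the last dose are covered (8%). In Group E the figure is 56 of 365 (15%).

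**4. What collection to Day 365 would add.** This assumes full retention, nominal visit days and all 60 subjects pooled.

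- Observed time now: 60 × 56/365.25 = 9.2 person-years.
- Observed time to Day 365: 60 × 365/365.25 = 60.0 person-years.
- With zero events, the one-sided 95% upper bound on a constant rate is −ln(0.05)/person-years, with −ln(0.05) = 2.996.
- Now: 2.996/9.2 = 0.33 per person-year. To Day 365: 2.996/60.0 = 0.05 per person-year.
- The period after Day 56 alone now has no observed time and so no bound of its own. With collection it has 60 × 309/365.25 = 50.8 person-years and a zero-event bound of 2.996/50.8 = 0.059 per person-year.

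**5. What it would not add.** With zero events, the bound on the proportion of subjects affected is 1 − 0.05^(1/n). This is 4.9% for n = 60 and 22.1% for n = 12, whatever the length of follow-up. Collecting for longer adds duration and no subjects.

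**The case against.** The strongest defence is that the cut-off is deliberate, consistent and matched to the objective. The primary objective concerns immunogenicity and safety 28 days after one or two vaccinations (protocol section 5.1), and the AE and SAE endpoints run to Day 56. That stands: the plan meets its own objective, and longer follow-up is an addition to it.

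A reader might infer that persistent joint symptoms would be lost. They would not be if they began by Day 56, because section 10.4 follows recorded events to the end of the study. Only later onset is missed.

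A reader might also link the AESI to the months-long joint disease described in section 4.2. Section 4.6 gives another basis: mild, transient arthralgia with an earlier live attenuated chikungunya vaccine. It adds that chikungunya-like symptoms are not expected from MV-CHIK. In the first phase I study, 10 of 42 subjects reported joint pain. In 5 of 42 it was rated as related, and all five cases were described as transient (section 4.4.1). The documents therefore give no particular reason to expect late-onset arthralgia.

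Late events do have some routes in. Section 14.2 has the investigator report to the ethics committee unexpected SAEs for which causality cannot be excluded, with no Day 56 limit. SAP section 6.2.2 allows AE outputs to be repeated if new events are reported. The study status listing in SAP section 7.2 has fields for an AE term and for death. All three depend on someone volunteering the information and do not replace asking every subject.

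**Conclusion.** The point holds for new-onset events. New SAEs and new arthralgia are not collected for 309 of 365 days (85%). Collection ends nominally 28 days (18 to 38) after the last MV-CHIK dose in Groups A-D and 56 days after the only dose in Group E.

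Three stronger statements are not supported. The plan does not contradict itself. It is not right that safety is known for only 28 days after the last dose, since Group E is observed for longer and events with earlier onset are followed on. The 4.9% bound does not measure the loss, since it is the same with or without the extra follow-up.

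The gain is in observed time, from about 9.2 to 60 person-years. The fall in the zero-event bound from about 0.33 to 0.05 per person-year assumes a constant rate, full retention and five pooled groups. Section 8.9.2 does not replace subjects who withdraw, so the time actually observed may be shorter. This is a cheap improvement that the sponsor should make, not a flaw in the primary analysis.

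**What to change.** At Visits 6 and 7, ask for and record SAEs and joint symptoms since the last visit, together with any other investigational product received. Ask about joint symptoms by name: arthralgia is not among the systemic symptoms listed for the diary in section 11.7, nor in Table 6.

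In the protocol, extend section 10.3 and footnote 3 of Table 2 to Day 365 for these events only. Bring sections 8.6.1, 8.6.2 and 10.2 into line. This would also provide a visit question for the follow-up to end of study that section 10.4 already requires. In the SAP, amend the matching footnote in section 1.6 and the cut-off statement in section 6.2.2, and add one table of post-Day 56 SAEs and AESIs to the final analysis. Routine non-serious AEs can stay limited to Day 56.

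The cost is a few questions at two existing visits, an amendment with the matching eCRF and SAP changes, and one table. Two drawbacks remain. Some late events will be hard to attribute when another trial product has been given. The sponsor staff who review them may already be unblinded after the Day 56 analysis (SAP section 2.4). That section does not unblind the site at that point, so the investigator's causality assessment could still be made blind.
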